10.7 Computerized Edit Checks

The database will incorporate the needed programmed edit checks to help ensure quality data. Messages to the mother may be generated automatically to alert her to any entry error.

10.8 Audit Trail

All entries and alterations made in the database will be captured by an audit trail in which the individuals accessing the database and providing entries and/or making alterations are identified via their user IDs and passwords.

11 Statistics

11.1 Sample Size Calculations

A sample size of 100 subjects is estimated to be sufficient to collect images of at least 200 pictures of diapers containing fecal (stool) material per score (type 1 to 7) of the BITSS plus 200 images of empty (no stool) disposable diapers.

Protocol V2 12OCT2018

Protocol V2 12OCT2018 ObvioHealth
The Digital Revolution Gets Clinical

12 Legal and Ethical Prerequisites

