- Two mothers who were not enrolled in the study will be provided a collection of study stool images and asked to rescore each image according to the BITSS

Statistical Considerations

A sample size of 100 subjects is estimated with the following considerations:

- Progression of potential subjects will be gated at the prescreening and screening steps to facilitate enrollment of an appropriately diversified set of infants/toddlers based on bowel patterns to reach 200 images per each stool consistency score (type 1 to 7) of the BITSS
- The Sponsor and ObvioHealth will review the distribution of the scores and image quality and will determine when the prescreening requirements can be modified
- A comparison will be made between the stool consistency scores from the mothers on-study to re-scores from mothers (not enrolled on-study) based only on the uploaded images

Protocol V2 12OCT2018

- Based on Sponsor review of the data, the following may be performed:
 - A post hoc analysis
 - Descriptive summary statistics for categorical and quantitative data
- The expectation is that not all the mothers will be compliant with study tasks for all 30 days
- A dropout rate of 15% is anticipated (if dropout rate exceeds 15%, replacements will be made for all additional withdrawals)

Protocol V2 120CT2018

5 Introduction

Accurately classifying stool consistency for infants and toddlers who are not yet toilet trained remains challenging. A recent study showed that among parents of infants and toddlers, only fair agreement existed between the parental report of stool consistency and the Bristol Stool Form Scale (BSS), ¹ a gold standard in the classification of stool consistency in adults and older children who are toilet trained. ² While there are alternative assessment methods which are used in clinical practice, such as the modified BSS and the Amsterdam Infant Stool Scale, a universally-accepted tool does not exist. ³ The Brussels Infant and Toddler Stool Scale (BITSS) was recently initiated based on the BSS to provide a classification tool to describe stool consistency for infants and toddlers. ⁴

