8.3 Subject Withdrawal Criteria

Mothers and their infants/toddlers may be withdrawn from the study at any time and for any reasons including but not limited to the following:

- 1) At their request or the request of their legally authorized representative.
- 2) If, in the PI's opinion, continuation in the study would be detrimental to the subject's well-being.
- 3) Poor compliance: if the mother and infant/toddler consistently do not adhere to the study procedures (per the PI's discretion).
- 4) Protocol deviation(s) which in the opinion of Sponsor warrant discontinuation from the study; e.g., violation of inclusion and/or exclusion criteria.

Study Note: If the infant/toddler experiences an illness (other than diarrhea/constipation) lasting longer than 7 days, has surgery or is admitted to the hospital for more than 24 hours, they should be withdrawn from the study immediately.

Due to the 15% dropout rate built into the estimated total sample size, subjects whose study participation is terminated prematurely for any of the above-listed criteria will not be replaced. If the dropout rate exceeds 15%, replacements will be made for all additional withdrawals. The PI will make every effort to contact subjects lost to follow-up during the study. Attempts to contact the subject will be documented in the subject's records (e.g., dates and times of attempted telephone contact).

Protocol V2 120CT2018

The number and percentage of subjects who withdraw early and their reasons for withdrawal will be presented in a table and a CONSORT flow diagram equivalent.

The following information will be documented in the mother and infant/toddler's record in the event of a subject's withdrawal from the study:

- I. Date of withdrawal
- II. Reasons for withdrawal

Even if consent is withdrawn, all data and all images that were acquired before consent was withdrawn will be maintained.

Protocol V2 12OCT2018

9 Assessment of Safety

As this is an observational study and the study procedures present no more than minimal risk, adverse events are not expected and therefore not collected or reported for this study.

Protocol V2 120CT2018

10 Execution of the Trial

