10.2 Data Collection

The mother will be asked to interact with the ClaimIt app daily for 30 days (or more) as follows:

- Stool images will be taken with a smartphone (or alternative suitable for capturing and transmitting high-quality, electronic images) and uploaded daily
- Every bowel movement will be photographed, potentially providing several images per day
 - Only 1 representative image per bowel movement should be transmitted
- If the mother has not uploaded an image in 24 hours, a notification and the Compliance eQuestionnaire requiring a response will be sent to her (Appendix IV)
- The following steps should be taken to ensure the image quality:
 - The picture should be taken in a well-lit room and with sufficient lighting on the diaper itself; pictures should not be taken in rooms requiring flash
 - The diaper should be placed on a table or area apart from any other objects;
 primarily only the soiled portion of the diaper should be in the picture
 - The diaper must be fully opened, and the contents must be clearly visible in the photograph

Protocol V2 120CT2018

- The camera should be zoomed-in as appropriate and focused on the stool itself
 - The image will include all the stool while excluding as much of the dry diaper as is reasonable
- The pictures should be taken within 10 minutes after the child has soiled the diaper
 - Images in which the stool form is not recognizable (e.g., stools that have been distorted or significantly smushed) should not be uploaded
- Along with each stool image uploaded, mothers will rate the stool consistency type compared to examples provided by the BITSS (Score 1 to 7)
 - Scoring will be based only on consistency, not color
 - Sample images of each score will be provided
- A total of two empty (no stool) disposable diapers, spread open, are to be submitted: one at Baseline and one at the End of Study
 - Images should be taken of the type of diaper used most frequently for the infant/toddler
 - Additional empty (no stool) disposable diaper images may only be submitted if the brand/type of diaper is changed; if only the diaper size changes, no additional pictures need to be uploaded

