#### 8.6 CONSORT diagram

Due to the 15% dropout rate built into the estimated total sample size, subjects whose study participation is terminated prematurely will not be replaced. The number and percentage of subjects who withdraw early will be presented in a CONSORT flow diagram equivalent; reasons for withdrawal will be presented in a table.

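### Protocol 11.1 calls 100 subjects enough for 200 empty-diaper images, but at the planned 15% dropout the upload schedule yields about 170 to 185

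*Protocol*

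**What the plan says.** Protocol 11.1 says that "A sample size of 100 subjects is estimated to be sufficient" to collect at least 200 stool images for each score "of the BITSS plus 200 images of empty (no stool) disposable diapers". Protocol 7.3 and SAP 6.3 make at least 200 empty-diaper images part of the primary endpoint, next to the seven stool counts.

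The supply of these images is set in Protocol 10.2 (repeated in SAP 7.1). Two per mother "are to be submitted: one at Baseline and one at the End of Study", and beyond that "Additional empty (no stool) disposable diaper images may only be submitted if the brand/type of diaper is changed"; a change of size alone does not call for another.

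On losses, the Statistical Considerations row of the Protocol synopsis states: "A dropout rate of 15% is anticipated". Protocol 8.3 explains non-replacement with the words "Due to the 15% dropout rate built into the estimated total sample size", and SAP 8.6 says that "subjects whose study participation is terminated prematurely will not be replaced". Replacement is foreseen only for withdrawals beyond 15%. Protocol 8.3 also provides that "all images that were acquired before consent was withdrawn will be maintained", so a Baseline image from a mother who later withdraws still counts.

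SAP 8.1 does not repeat the sufficiency claim. It describes 100 subjects with about 15% withdrawal as predetermined, without a formal calculation.

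**The concern.** Two images from each of 100 mothers is exactly the target, so the stated size has no reserve for this count. The same plan assumes that 15 of the 100 will leave early, and the second image is scheduled for the end of participation. The plan's inputs therefore do not support its sufficiency statement.

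At stake is one of eight counts in the primary endpoint. Enrollment could also close before the gap is noticed. The Study Population rows of both synopses run enrollment until the stool-score counts are reached and do not mention empty diapers. The gating in Protocol 10.1 likewise follows the child's usual stool consistency. Seven targets could be met with the eighth still short. Extending a mother's participation (Protocol 7.5) brings more stool images but no further scheduled empty-diaper image.

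**Working it through.** **Inputs**
- Enrolled subjects N = 100 (Protocol 11.1).
- Scheduled empty-diaper images per mother: 2 (Protocol 10.2).
- Dropout d = 0.15, inside the 100 and not replaced (Protocol synopsis and 8.3; SAP 8.1 and 8.6).
- Target: 200 (Protocol 7.3).

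**The plan's figure.** With d = 0 and every upload made, 2 × 100 = 200. The stated sufficiency is reproduced only if all 100 mothers send both images.

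**With the plan's dropout**
- Every dropout sends the Baseline image only: N + N(1 − d) = 100 + 85 = 185. Shortfall 200 − 185 = 15 (7.5% of the target).
- Dropouts send none: 2N(1 − d) = 2 × 85 = 170. Shortfall 200 − 170 = 30 (15% of the target).

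| Dropout | All dropouts send Baseline only | Dropouts send none |
|---|---|---|
| 0% | 200 | 200 |
| 5% | 195 | 190 |
| 10% | 190 | 180 |
| 15% | 185 | 170 |

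**Closing images from withdrawing mothers.** The documents do not say whether a mother who withdraws is asked for the End of Study image. If all 15 sent the Baseline image and a share f also send a closing one, the count is 185 + 15f. That is about 192 at f = 0.5 and 200 only at f = 1. The value of f is not given.

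**Brand or type changes.** To close the gap alone, these would have to supply 15/100 = 0.15 to 30/100 = 0.30 extra images per enrolled mother. No rate is given.

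**Enrollment for an expected 200 at 15% dropout**
- At 1.85 images per enrolled mother: 108 × 1.85 = 199.8 and 109 × 1.85 = 201.7 (rounded), so 109.
- At 1.70 images per enrolled mother: 117 × 1.70 = 198.9 and 118 × 1.70 = 200.6, so 118.

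That is 9 to 18 more than 100.

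**Alternative reading.** If the 100 were completers, 100/0.85 rounds up to 118 enrolled and the target would be met. Protocol 8.3 and SAP 8.1 rule this out, because both put the 15% inside the 100.

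**The case against.** The strongest reply is that the sentence is an estimate and the plan has ways to correct it. Protocol 10.1 lets enrollment be expanded until target values are attained, without limiting which targets. The synopses say approximately 100, and the sponsor and CRO review images weekly. Brand-change images are allowed, and at 0.15 per mother they would close the gap in the 185 case. The later SAP already drops the sufficiency claim, and SAP 8.2 plans no analysis of the count.

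Most of this stands as a reason to rate the point low. It does not make the sentence right: expansion means more than 100 subjects, and without a rate for brand changes the documents do not support sufficiency on that ground. The expansion clause can be read to include empty diapers, and the adaptive-recruitment sentence in Protocol 10.1 speaks of each type without the word stool. But that sentence sits in text about stool gating, its synopsis counterpart names stool types, and no passage expressly links expansion to the empty-diaper count.

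A second reply is that 170 is an extreme. A pair is enrolled only after the mother has uploaded three scored test images, so it is unlikely that all 15 dropouts would skip the Baseline upload. That is fair, and 185 is the more natural figure if withdrawing mothers send no closing image. But 170 is not a floor either: the synopsis expects that not all mothers will be compliant throughout, and missed uploads by completers are not counted here.

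**Conclusion.** The concern holds, as a minor error in a stated figure. On scheduled uploads and the plan's own 15% dropout, 100 enrolled subjects give about 170 to 185 empty-diaper images, 15 to 30 short of the target.

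The range assumes that completers send both images, that withdrawing mothers send no closing image, and that brand or type changes add none. The first assumption favours the plan; the other two work against it, and the documents give no figure for either. The arithmetic is certain; how far those two sources would fill the gap is not. The endpoint can still be met through expansion, but then with more than the stated 100 subjects.

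**What to change.** - **Protocol 11.1:** leave the stool part as it is. Replace the empty-diaper part with wording such as: *With 15% dropout, 100 enrolled subjects are expected to give about 170 to 185 scheduled empty-diaper images, plus any sent after a change of diaper brand or type; enrollment may be expanded if 200 is not reached.*
- **Protocol 10.1:** state that the target values that govern expansion include the 200 empty-diaper images.
- **Study Population rows of the Protocol and SAP synopses:** add that enrollment may also be expanded to reach 200 empty-diaper images.
- **Protocol 7.1:** for consistency, add the empty-diaper row (Baseline and End of Study) that the SAP 6.1 calendar already has. The arithmetic does not depend on this.

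No participant task or upload schedule changes, so the correction also works for mothers already past Baseline (SAP 8.4 shows that images had been collected by 18NOV2018). The costs are a less favourable stated figure and an amendment that must be notified to the IRB/EC under Protocol 12.2.3. Re-consent may follow: 12.2.3 says subjects must re-sign after an approved amendment, while 13.3 says they may be required to. If expansion is used for empty diapers alone, expect about 9 to 18 more mothers at 15% dropout.

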12.1 Legal Requirements

The study will initiate after approval from the IntegReview IRB which follows the guidance of USA regulatory bodies and general Good Clinical Practice (GCP)/International Conference on Harmonisation (ICH) regulations.

12.2 Ethical Aspects

12.2.1 Protection of the Subject's Confidentiality

Confidentiality of all study participants will be maintained; codes for subject identification will be utilized. Subjects will review and complete the HIPAA release of information form during the eIC process.

12.2.2 Informed Consent

Electronic Informed Consent (eIC) signed by the subject indicating their consent to her and her infant/toddler's participation in the study is required. This will be completed prior to conducting any study-related activities and will be done in accordance with all applicable regulatory requirements.

The eIC will inform the mother about all aspects of study participation. Dedicated study personnel will be available to the parent to answer questions about the study or the informed consent. The IRB/EC will approve the eIC. Any amendments to these documents must be approved by the IRB/EC.

The mother must sign the eIC prior to the initiation of any study-related activities beyond prescreening.

The decision to participate in the study is entirely voluntary. The PI and/or his/her designee must emphasize to the mother that the consent to participate can be withdrawn at any time without penalty or loss of benefits to which the mother and infant/toddler are otherwise entitled.

Protocol V2 120CT2018

12.2.3 Ethics Committee Approval

The study protocol will be submitted by the PI (or designee) for examination by the US Institutional Review Board (IRB)/EC. Commencement of the clinical trial is not permitted without written approval of the IRB/EC.

The IRB/EC must be notified of all subsequent additions or changes in the study protocol. If a protocol amendment is made and approved by the IRB/EC, subjects must re-sign the ICF after review to remain in the trial.

12.2.4 Declaration of Helsinki

This trial will be conducted according to the principles and rules laid down in the Declaration of Helsinki and its subsequent amendments.

Protocol V2 120CT2018

13 Quality Control and Quality Assurance

13.1 **Monitoring**

Since there are no physical sites involved in this protocol, monitoring will be implemented throughout the study via remote data reviews. The monitor will check eCRF data for completeness and consistency.

The main protocol deviations for consideration on this trial are:

- Informed consent process not adequately performed
- Violation of inclusion and/or exclusion criteria
- Non-compliance with study-related daily requirements
- Any other GCP non-compliance

Protocol deviations will be tracked and logged in the Protocol Deviation Log.

At the end of the trial, the Monitor and/or Clinical Data Manager (CDM) will ensure that all documentation and the trial master file (TMF) are complete. In all cases, it is the responsibility of the CPM, CDM and study team to maintain subject confidentiality.

13.2 Quality Control

13.2.1 Quality Control of Essential Documents

ObvioHealth will implement and maintain quality assurance, and quality control systems with Standard Operating Procedures (SOPs) to ensure that this clinical trial is conducted, and data are generated, documented (recorded) and reported in compliance to the protocol, GCP/ICH standards, and other applicable local regulations.

13.3 Responsibilities of the PI

The PI is responsible for the following:

 Selection of participants/subjects in accordance with the inclusion and exclusion criteria (in this study the mother and infant/toddler)

Protocol V2 120CT2018

- Maintain confidentiality and safety of subjects in accordance with the Declaration of Helsinki
- Adherence to the study protocol and the spirit of GCP
- If modification becomes necessary, the rationale will be provided in a protocol amendment signed by the PI and Sponsor for submission to the IRB/EC
 - After the protocol amendment approval, subjects may be required to re-sign the eIC to remain in the trial
- During the trial, provide subjects with any newly available information that may be relevant to them
- Cooperation in the case of an audit and/or a regulatory inspection, providing direct access to data and/or documents

Protocol V2 120CT2018

14 Study End Procedures

APPENDIX I: Brussels Infant and Toddler Stool Scale (BITSS)

Refer to the following BITSS (Score 1 to Score 7) images in order to rate each stool image prior to uploading through the ClaimIt app:

Protocol V2 12OCT2018

APPENDIX II: Prescreening eQuestionnaire

Date:				
Mother				
Name: (First and Last)				
Relationship to Infant:	_Mother			
Date of Birth:	(exclu	uded if not ≥18 v	years of age)	
Phone: (best # to call)				
Best time of day to call:	Morning	Afternoon	Evening	Other (open ended)
Email:				
Confirm Email:				
Infant/Toddler				
Name (First and Last)		Gender:	Boy or	_ Girl
Date of Birth:	(exclu	uded if not in ag	e group 0-24	months at time of
enrollment)				
The following is a question	naire to help u	ıs better unders	tand you and	your child; this will help us
determine if this	study is right	for you. Please	pick the best	answer choice.
1. Do you or your child ha	ve a significan	t limitation (inc	luding medica	al or physical concerns,
travel, etc.), which may	interfere with	n daily study pai	ticipation for	30 days in a row?
a. Yes (exclusion)				
b. No				
c. Don't Know/Not Sui	re (exclusion)			

Protocol V2 12OCT2018

[figure not shown]

- 2. Do you live in a household where you have an easy, reliable access, 24-hours per day to the internet, and do you also have one or more of the following electronic devices: tablet or smartphone?
 - a. Yes
 - b. No (exclusion)
- 3. Is the smartphone or tablet being used to capture and upload images for this study more than 4 years old?
 - a. Yes (exclusion)
 - b. No
- 4. Are you now using, or are you willing to use, disposable diapers for your child?
 - a. Yes
 - b. No (exclusion)

Protocol V2 12OCT2018

- 5. Using the images below, please select: (formatted as two questions in ClaimIt)
 - a. Your child's most frequent stool consistency
 - b. Your child's **second** most frequent stool consistency

Protocol V2 120CT2018

6. Does your child experience the following (liquid or hard stools) at least once a week?

- a. Yes, both
- b. Yes, liquid stools
- c. Yes, hard stools
- d. No

IF YOU HAVE ANY QUESTIONS OR PROBLEMS COMPLETING AND/OR SUBMITTING THIS

QUESTIONNAIRE, PLEASE CALL US AT: 1-XXX-XXXX

Protocol V2 120CT2018

APPENDIX III: Screening eQuestionnaire

Date:
Mother (Info below was also collected at prescreening, verify accuracy)
Name (First and Last):
Relationship to Infant:Mother
Date of Birth: (excluded if not ≥18 years of age)
Phone: (best # to call)
Best time of day to call:MorningAfternoonEveningOther (open ended)
Address: (# and street)
(City, State, Zip Code)
Email:
Infant/Toddler (Info below was also collected at prescreening, verify accuracy)
Name (First and Last) Gender:Boy or Girl
Date of Birth: (excluded if not in age group 0-24 months at time of enrollment)
The following is a questionnaire to help us better understand you and your child; this will help us determine if this study is right for you. Please pick the best answer choice.
 Does your child consume standard food (breastmilk; formula; commercial/homemade baby,
table or finger food) appropriate for their age?
a. Yes
b. No (exclusion)
2. Do you or your child have a significant limitation (including medical or physical concerns,
travel, etc.), which may interfere with daily study participation for 30 days in a row?
a. Yes (exclusion)
b. No
c. Don't Know/Not Sure (exclusion)

Protocol V2 12OCT2018

- 3. Do you live in a household where you have reliable, easy access to the internet and electronic devices such as a smartphone or tablet?
 - a. Yes
 - b. No (exclusion)
- 4. Is the smartphone/tablet being used capable of capturing and sending high quality electronic images?
 - a. Yes
 - b. No (exclusion)

IF YOU HAVE ANY QUESTIONS OR PROBLEMS COMPLETING AND/OR SUBMITTING THIS

QUESTIONNAIRE, PLEASE CALL US AT: 1-XXX-XXXX

Protocol V2 12OCT2018

APPENDIX IV: Compliance eQuestionnaire

To be sent to participant when no image has been uploaded for >24 hours.

1.	Did your child produce a stool in the last 24 hours? a. Yes b. No
	(If yes) Please remember that images should be taken and uploaded no longer than 10 minutes after your child has soiled the diaper, unless the stool was significantly smushed.
	(If no) Why did your child not have stool in the last 24 hours?Probably constipatedI don't knowOther (Open ended)

Protocol V2 12OCT2018

